5.1.3 Presentation of results

Tables will present TEAEs only. The AEs will be presented for the overall study duration, including AEs during the follow up. Pre-treatment AEs will only be listed.

An overview table will show the number and percentage of patients with at least 1 event and the number of events for the following:

- TEAEs
- Serious TEAEs
- Non serious TEAEs
- Grade \geq 3 TEAEs
- Fatal TEAEs
- Treatment related TEAEs according to the principle investigator
- Procedures related TEAEs
- Serious treatment related TEAEs
- TEAEs for which the study was discontinued
- TEAEs for which the study drug was discontinued
- TEAEs for which the study drug was interrupted
- TEAEs of special interest: bleeding events
- TEAEs of special interest: infections
- IRR events

In addition, the number of events per patient years on study will be added to the overview table.

SGS	Statistical Analysis Plan	
ARGX-113-1801	Final analysis	Final 1.0 of 28MAR2022

Summary tables by MedDRA SOC and PT will show the number and percentage of patients with at least 1 event. The table of TEAEs will additionally show the number of events.

Separate tables will be prepared for the following TEAEs:

- Serious TEAEs
- Non serious TEAEs
- Grade \geq 3 TEAEs
- Fatal TEAEs
- Treatment related TEAEs according to the Principle Investigator
- Procedures related TEAEs
- Serious treatment related TEAEs
- TEAEs for which the study was discontinued
- TEAEs for which the study drug was discontinued
- TEAEs for which the study drug was interrupted
- TEAEs of special interest
- IRR events
- Serious IRR events
- Hypersensitivity events

Tables on TEAEs, serious TEAEs and hypersensitivity events will be repeated by ADA patient classification and by NAb patient classification.

All AEs, including pre-treatment events will be listed.

5.2 CLINICAL LABORATORY EVALUATION

5.2.1 Available data

Per CTP, the following laboratory parameters are expected:

- Biochemistry: creatinine, creatinine clearance (BSA adjusted), blood urea nitrogen (BUN), alanine aminotransferase (ALT), aspartate aminotransferase (AST), total bilirubin, gamma-glutamyl transferase (GGT), C-reactive protein (CRP), alkaline phosphatase (ALP), lactate dehydrogenase (LDH), uric acid, albumin, potassium, sodium, total calcium.
- Hematology: hemoglobin, white blood cell (WBC) count with WBC differentials.
- Urinalysis: color, clarity/appearance, specific gravity, pH, protein, glucose, ketones, blood, bilirubin, urobilinogen, nitrite, leukocyte esterase, and microscopic examination including red blood cell (RBC) count, WBC, casts, crystals, bacteria.

Normal ranges are available as provided by the laboratory.

SGS	Statistical Analysis Plan	
ARGX-113-1801	Final analysis	Final 1.0 of 28MAR2022

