# 13. APPENDICES

# Appendix 1 Laboratory Evaluations

Hematology	Hemoglobin, white blood cell (WBC) count with WBC differential		
Coagulation	activated partial thromboplastin time (aPTT), prothrombin time (PT INR)		
Clinical Chemistry	Creatinine, creatinine clearance, blood urea nitrogen (BUN), alanine aminotransferase (ALT), aspartate aminotransferase (AST), total bilirubin, gamma-glutamyl transferase (GGT), C-reactive protein (CRP), alkaline phosphatase (ALP), lactate dehydrogenase (LDH), uric acid, albumin, potassium, sodium, calcium		
Urinalysis	Color, clarity/appearance, specific gravity, pH, protein, glucose, ketones, blood, bilirubin, urobilinogen, nitrite, leukocyte esterase, and microscopic examination including red blood cell (RBC) count, WBC, casts, crystals, bacteria		
Serology	Human immunodeficiency virus (HIV) antibodies (1 and 2), hepatitis B surface antigen (HBsAg), antibodies to the surface and core antigens of the hepatitis B virus (anti-HBs and anti-HBc), hepatitis C virus antibody (HCV-Ab)		
Other	Serum human chorionic gonadotrophin (ß-HCG), follicle-stimulating hormone (FSH) test, autoimmune antibody testing, antinuclear antibody, thyroglobulin, thyroid stimulating hormone (TSH), tuberculosis QuantiFERON test		
Pharmacokinetics	Serum levels of efgartigimod		
Pharmacodynamic markers	Serum levels of total IgG and IgG subtypes (IgG1, IgG2, IgG3, and IgG4)		
Antiplatelet antibodies	Presence, nature, and level of antiplatelet antibodies		
Anti-drug antibodies	Serum levels of anti-ARGX-113 binding antibodies, neutralizing antibodies (Nab)		
Local evaluations	Platelet count urine pregnancy		
Other exploratory	Whole blood flow cytometry for		

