5.2.2 Derivation rules

The following parameters will be derived:

- Estimated glomerular filtration rate (eGFR) (Chronic Kidney Disease Epidemiology Collaboration (CKD-EPI)) (mL/min/1.73m²) = 141 * minimum(creatinine (mg/dL)/ K; 1)^{α} * maximum(creatinine (mg/dL)/K; 1)^{-1.209} * 0.993 ^{age (years)} * [1.018 if female] * [1.159 if race = black] where K = 0.7 if female and K = 0.9 if male; α = -0.329 if female and α = -0.411 if male
- The following abnormality categories will be defined:
 - Low: value < lower limit of normal range
 - $\circ \quad \text{Normal: lower limit of normal range} \leq \text{value} \leq \text{upper limit of normal range}$
 - High: value > upper limit of normal range

Note:

- Classification will be done in standardized units, using non-imputed values and limits.
- For the worst-case analysis visits, as defined in section 2.2.5, an additional category low + high is defined in case there are both low and high post-baseline values.

Toxicity grades will be computed according to the NCI CTCAE toxicity grading list (version 5.0^5). The implementation of these toxicity grades for analysis is presented in appendix 9.2. Additional study-specific toxicity gradings will be applied as defined in appendix 9.3. Only the parameters described in appendices 9.2 and 9.3 will be computed, according to the declared limits for each grade.

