9.2 TOXICITY GRADES (CTCAE, v5.0)

Below table documents how the Common Terminology Criteria for Adverse Events CTCAE, v5.0: November 27, 2017 is implemented in the statistical analysis.

PARAMETER	Unit	GRADE 1	GRADE 2	GRADE 3	GRADE 4
Amylase (pancreatic)		>1.0-1.5 *ULN	>1.5-2.0 *ULN	>2.0-5.0 *ULN	>5.0 *ULN
Alanine amino transferase		>1-3 *ULN	>3-5 *ULN	>5-20 *ULN	>20 *ULN
Albumin ^[1]	g/L	<lln-30< td=""><30-20	<20	-	</lln-30<>	<30-20	<20	-
	g/dL	<lln-3< td=""><3-2	<2	-	</lln-3<>	<3-2	<2	-
Alkaline phosphatase		>1.0-2.5 *ULN	>2.5-5.0 *ULN	>5.0-20.0 *ULN	>20.0 *ULN
Aspartate amino transferase		>1-3 *ULN	>3-5 *ULN	>5-20 *ULN	>20 *ULN
Bilirubin (total)		>1.0-1.5 *ULN	>1.5-3.0 *ULN	>3.0-10.0 *ULN	>10.0 *ULN
Calcium low ^[1]	mmol/L	<lln-1.0< td=""><1.0-0.9	<0.9-0.8	<0.8	</lln-1.0<>	<1.0-0.9	<0.9-0.8	<0.8
	mg/dL	<lln-4.0< td=""><4.0-3.6	<3.6-3.2	<3.2	</lln-4.0<>	<4.0-3.6	<3.6-3.2	<3.2
Calcium high ^[1]	mmol/L	>ULN-1.5	>1.5-1.6	>1.6-1.8	>1.8
	mg/dL	>ULN-6.0	>6.0-6.4	>6.4-7.2	>7.2
Calcium (corrected) low [1]	mmol/L	<lln-2.00< td=""><2.00-1.75	<1.75-1.50	<1.50	</lln-2.00<>	<2.00-1.75	<1.75-1.50	<1.50
	mg/dL	<lln-8< td=""><8-7	<7-6	<6	</lln-8<>	<8-7	<7-6	<6
Calcium (corrected) high [1]	mmol/L	>ULN-2.9	>2.9-3.1	>3.1-3.4	>3.4
	mg/dL	>ULN-11.5	>11.5-12.5	>12.5-13.5	>13.5
Cholesterol ^[1]	mmol/L	>ULN-7.75	>7.75-10.34	>10.34-12.92	>12.92

SGS	Statistical Analysis Plan	
ARGX-113-1801	Final analysis	Final 1.0 of 28MAR2022

	mg/dL	>ULN-300	>300-400	>400-500	>500
Creatine kinase		>1.0-2.5 *ULN	>2.5-5.0 *ULN	>5.0-10.0 *ULN	>10.0 *ULN
Creatinine		>1.0-1.5 *ULN	>1.5-3.0 *ULN	>3.0-6.0 *ULN	>6.0 *ULN
Gamma-glutamyl transferase		>1.0-2.5 *ULN	>2.5-5.0 *ULN	>5.0-20.0 *ULN	>20.0 *ULN
Glucose (fasting) low ^[1,2]	mmol/L	<lln-3.0< td=""><3.0-2.2	<2.2-1.7	<1.7	</lln-3.0<>	<3.0-2.2	<2.2-1.7	<1.7
	mg/dL	<lln-55< td=""><55-40	<40-30	<30	</lln-55<>	<55-40	<40-30	<30
Lipase		>1.0-1.5 *ULN	>1.5-2.0 *ULN	>2.0-5.0 *ULN	>5.0 *ULN
Magnesium low ^[1]	mmol/L	<lln-0.5< td=""><0.5-0.4	<0.4-0.3	<0.3	</lln-0.5<>	<0.5-0.4	<0.4-0.3	<0.3
	mg/dL	<lln-1.2< td=""><1.2-0.9	<0.9-0.7	<0.7	</lln-1.2<>	<1.2-0.9	<0.9-0.7	<0.7
Magnesium high ^[1]	mmol/L	>ULN-1.23	-	>1.23-3.30	>3.30
	mg/dL	>ULN-3.0	-	>3.0-8.0	>8.0

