Potassium low ^[1]	mmol/L	-	<lln-3.0< td=""><3.0-2.5	<2.5	</lln-3.0<>	<3.0-2.5	<2.5
	mEq/L	-	<lln-3.0< td=""><3.0-2.5	<2.5	</lln-3.0<>	<3.0-2.5	<2.5
Potassium high ^[1]	mmol/L	>ULN-5.5	>5.5-6.0	>6.0-7.0	>7.0
	mEq/L	>ULN-5.5	>5.5-6.0	>6.0-7.0	>7.0
Sodium low ^[1]	mmol/L	<lln-130< td="">-	<130-120	<120	</lln-130<>	-	<130-120	<120
	mEq/L	<lln-130< td="">-	<130-120	<120	</lln-130<>	-	<130-120	<120
Sodium high ^[1]	mmol/L	>ULN-150	>150-155	>155-160	>160
	mEq/L	>ULN-150	>150-155	>155-160	>160
Triglycerides	mmol/L	1.71-3.42	>3.42-5.70	>5.70-11.4	>11.4
	mg/dL	150-300	>300-500	>500-1000	>1000

SGS	Statistical Analysis Plan	
ARGX-113-1801	Final analysis	Final 1.0 of 28MAR2022

Partial thromboplastin time (activated or not specified		>1.0-1.5 *ULN	>1.5-2.5 *ULN	>2.5 *ULN	-
CD4 count ^[1]	giga/L	<lln-0.50< td=""><0.50-0.20	<0.20-0.05	<0.05	</lln-0.50<>	<0.50-0.20	<0.20-0.05	<0.05
	counts/mm ³	<lln-500< td=""><500-200	<200-50	<50	</lln-500<>	<500-200	<200-50	<50
Fibrinogen		<1.00-0.75 *LLN	<0.75-0.50 *LLN	<0.50-0.25 *LLN	<0.25 *LLN
International normalized ratio		>1.2-1.5 *ULN	>1.5-2.5 *ULN	>2.5 *ULN	-
Lymphocytes (absolute count) low [1]	giga/L	<lln-0.80< td=""><0.80-0.50	<0.50-0.20	<0.20	</lln-0.80<>	<0.80-0.50	<0.50-0.20	<0.20
	counts/mm ³	<lln-800< td=""><800-500	<500-200	<200	</lln-800<>	<800-500	<500-200	<200
Lymphocytes (absolute count) high	giga/L	-	>4-20	>20	-
	counts/mm ³	-	>4000-20000	>20000	-
Neutrophils (absolute count) ^[1]	giga/L	<lln-1.5< td=""><1.5-1.0	<1.0-0.5	<0.5	</lln-1.5<>	<1.5-1.0	<1.0-0.5	<0.5
	counts/mm ³	<lln-1500< td=""><1500-1000	<1000-500	<500	</lln-1500<>	<1500-1000	<1000-500	<500
Platelets ^[1]	giga/L	<lln-75< td=""><75-50	<50-25	<25	</lln-75<>	<75-50	<50-25	<25
	counts/mm ³	<lln-75000< td=""><75000-50000	<50000-25000	<25000	</lln-75000<>	<75000-50000	<50000-25000	<25000
White blood cells ^[1]	giga/L	<lln-3< td=""><3-2	<2-1	<1	</lln-3<>	<3-2	<2-1	<1
	counts/mm ³	<lln-3000< td=""><3000-2000	<2000-1000	<1000	</lln-3000<>	<3000-2000	<2000-1000	<1000

^[1] In case ULN/LLN is higher/lower than the upper/lower limit of grade 1 (or even higher grades), ULN/LLN will be ignored and only the fixed values of CTCAE will be considered.

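### The SAP assigns total calcium to no toxicity-grading row; the row that matches by name would grade ordinary values as grade 4 high

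*SAP*

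**What the plan says.** The biochemistry list in SAP 5.2.1 closes with "uric acid, albumin, potassium, sodium, total calcium". Protocol Appendix 1 has "uric acid, albumin, potassium, sodium, calcium", without saying which form of calcium. Neither lists another calcium measure. Albumin is in the same panel.

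SAP 5.2.2 derives eGFR and the low/normal/high categories. It has no corrected-calcium derivation. On grading it says: "Only the parameters described in appendices 9.2 and 9.3 will be computed, according to the declared limits for each grade".

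Appendix 9.2 has an unqualified 'Calcium' entry and a 'Calcium (corrected)' entry, each with a low and a high direction. For 'Calcium' high, grades 1 to 4 are ">ULN-1.5 >1.5-1.6 >1.6-1.8 >1.8" in mmol/L and ">ULN-6.0 >6.0-6.4 >6.4-7.2 >7.2" in mg/dL. For "Calcium (corrected) high" they are ">ULN-2.9 >2.9-3.1 >3.1-3.4 >3.4" in mmol/L. Footnote 1, attached to all these rows, covers a normal limit lying beyond the grade 1 limit: "ULN/LLN will be ignored and only the fixed values of CTCAE will be considered".

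Under SAP 5.2.3 the grades feed a shift table against baseline, shown separately for low and high. This is Table 14.3.2.3, marked topline in section 8.1.

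**The concern.** The two entries are plainly on different scales. The corrected row starts low grade 4 below 1.50 mmol/L, whereas the unqualified row allows high grade 1 up to 1.5 mmol/L. One measurement cannot be gradable on both, so the SAP has to say which entry applies to the one calcium that is collected. It does not. A programmer who matches by name will use 'Calcium', because the measurement is uncorrected and nothing sends it to the other row.

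At stake is the calcium part of one topline safety table. If nearly everyone is already grade 4 high at baseline, no high grade can count as treatment-emergent, because the SAP's definition requires that it was absent at baseline. In the low direction, moderate and severe falls would be compressed into grade 1.

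**Working it through.** **Inputs (SAP Appendix 9.2, mmol/L).**

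| Entry | Grade 1 | Grade 2 | Grade 3 | Grade 4 |
|---|---|---|---|---|
| Calcium, low | below LLN to 1.0 | below 1.0 to 0.9 | below 0.9 to 0.8 | below 0.8 |
| Calcium, high | above ULN to 1.5 | above 1.5 to 1.6 | above 1.6 to 1.8 | above 1.8 |
| Corrected, low | below LLN to 2.00 | below 2.00 to 1.75 | below 1.75 to 1.50 | below 1.50 |
| Corrected, high | above ULN to 2.9 | above 2.9 to 3.1 | above 3.1 to 3.4 | above 3.4 |

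The laboratory's normal range is not in the documents. Three ranges were assumed: 2.05–2.50, 2.15–2.55 and 2.20–2.65 mmol/L.

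**Step 1: could the limits be a misprint in one unit?** Divide the mg/dL limit by the mmol/L limit. 'Calcium' high: 6.0/1.5 = 6.4/1.6 = 7.2/1.8 = 4.0. 'Calcium' low: 4.0/1.0 = 3.6/0.9 = 3.2/0.8 = 4.0. Corrected low: 8/2.00 = 7/1.75 = 6/1.50 = 4.0. Corrected high: 11.5/2.9 = 3.97, 12.5/3.1 = 4.03, 13.5/3.4 = 3.97. The units agree in all four rows, so the unqualified limits stand as declared.

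**Step 2: apply footnote 1 to the 'Calcium' row.** Every assumed ULN (2.50 to 2.65) is above 1.5, and above 1.8 as well. The ULN is therefore ignored and 1.5, 1.6 and 1.8 apply alone. Every assumed LLN (2.05 to 2.20) is above 1.0, so the footnote does not remove it: low grade 1 runs from the LLN down to 1.0.

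**Step 3: grade the same values on both entries.** Results are the same under all three ranges except where marked.

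| Total calcium (mmol/L) | 'Calcium' row | 'Calcium (corrected)' row |
|---|---|---|
| 1.40 | low 1 | low 4 |
| 1.55 | low 1 and high 2 | low 3 |
| 1.70 | low 1 and high 3 | low 3 |
| 1.85 | low 1 and high 4 | low 2 |
| 1.99 | low 1 and high 4 | low 2 |
| 2.05 | high 4 (plus low 1 if LLN is 2.15 or 2.20) | none (low 1 if LLN is 2.15 or 2.20) |
| 2.20, 2.40, 2.50 | high 4 | none |
| 3.0 | high 4 | high 2 |
| 3.5 | high 4 | high 4 |

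**Step 4: the general statement.** The corrected row gives at most grade 1 anywhere from 2.00 to 2.9. Since 2.00 > 1.8, all of that interval is grade 4 high on the unqualified row. On that row a value escapes grading only if it is at or above the LLN and at or below 1.5, which is impossible for any LLN above 1.5.

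**Step 5: carry it to the table.** The worst case is the highest grade per parameter and direction (SAP 2.2.5). A patient who is grade 4 high at baseline stays in one cell of the high-direction shift table whatever happens later.

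**The case against.** The strongest reply is that no sentence in the SAP puts total calcium on the unqualified row. Appendix 9.2 reads as a standard list. It includes lipase, magnesium, cholesterol, creatine kinase, triglycerides, fibrinogen and CD4 count, none of which is in the 5.2.1 list, so a row's presence does not show that it will be used. This stands, and the conclusion has to be conditional. It does not remove the problem. Those other rows match nothing in the 5.2.1 list, whereas 'Calcium' matches a measured parameter by name. If the row is treated as unused, total calcium has no row at all.

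A reader might infer that a calcium signal would be lost altogether. The documents do not support that. Table 14.3.2.1 gives values and changes from baseline. Table 14.3.2.2 classifies results against the laboratory's own range and counts treatment-emergent abnormalities. Listing 16.2.8.1 shows results for patients with abnormal values. None of these uses Appendix 9.2.

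A reader might also infer that low values simply become high ones. That is only partly so. The directions are shown separately, so a value between 1.5 and 2.00 mmol/L also carries low grade 1, and a value of 1.5 or less gets no high grade.

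It is tempting to call the unqualified row ionised calcium. The SAP never labels it so, and the point does not need it.

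Finally, the effect would be alike in both arms and conspicuous, and SAP 1.8 has tables reviewed by an independent person. It would probably be noticed. The remedy would then be chosen without a prespecified rule.

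**Conclusion.** The point holds as a gap in the grading rules with a definite bad outcome on the most literal reading. On the 'Calcium' row, every value from 2.00 to 2.9 mmol/L is grade 4 high, so close to all patients would be grade 4 at baseline and afterwards, and low grades 2 to 4 would need values below 1.0 mmol/L. On the other reading calcium has no valid toxicity grade. Either way the calcium part of topline Table 14.3.2.3 is uninterpretable or empty, and it could not show a treatment-emergent high grade.

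The high-grade result needs only that the ULN exceeds 1.5 mmol/L. The low grade 1 between 1.5 and 2.00 mmol/L needs an LLN of at least 2.00. Both hold under all three assumed ranges. The matter is confined to one parameter in one safety display and touches no efficacy analysis. It should still be corrected, because following the declared limits yields a wrong table.

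**What to change.** In SAP 5.2.2, do one of two things. Either derive albumin-corrected calcium, giving the formula, its units and what happens when albumin is missing, and grade it on the 'Calcium (corrected)' row; or state that total calcium is graded on that row without correction. In Appendix 9.2, add a note that the unqualified 'Calcium' row is not applied to total calcium in this trial.

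The cost is a line or two of SAP text and, for the first option, one derived laboratory parameter. Albumin and calcium are already in the same chemistry panel, so no new data or visits are needed. The documents give no correction formula, so the sponsor has to supply one if it takes that option.

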5.2.2 Derivation rules

The following parameters will be derived:

- Estimated glomerular filtration rate (eGFR) (Chronic Kidney Disease Epidemiology Collaboration (CKD-EPI)) (mL/min/1.73m²) = 141 * minimum(creatinine (mg/dL)/ K; 1)^{α} * maximum(creatinine (mg/dL)/K; 1)^{-1.209} * 0.993 ^{age (years)} * [1.018 if female] * [1.159 if race = black] where K = 0.7 if female and K = 0.9 if male; α = -0.329 if female and α = -0.411 if male
- The following abnormality categories will be defined:
 - Low: value < lower limit of normal range
 - $\circ \quad \text{Normal: lower limit of normal range} \leq \text{value} \leq \text{upper limit of normal range}$
 - High: value > upper limit of normal range

Note:

- Classification will be done in standardized units, using non-imputed values and limits.
- For the worst-case analysis visits, as defined in section 2.2.5, an additional category low + high is defined in case there are both low and high post-baseline values.

Toxicity grades will be computed according to the NCI CTCAE toxicity grading list (version 5.0^5). The implementation of these toxicity grades for analysis is presented in appendix 9.2. Additional study-specific toxicity gradings will be applied as defined in appendix 9.3. Only the parameters described in appendices 9.2 and 9.3 will be computed, according to the declared limits for each grade.

5.2.3 Presentation of results

The statistical analysis will present results in standardized units, except for eGFR, which will be reported in mL/min/ $1.73m^2$.

Continuous laboratory parameters will be summarized by means of descriptive statistics at each analysis visit. Actual values and changes from baseline will be shown in the same table. Categorical urinalysis results will be listed only.

Laboratory abnormalities will be presented as cross-tabulations of the abnormality at each post-baseline analysis visit and at the worst-case analysis visit versus the baseline abnormality. Numbers of patients with treatment-emergent abnormalities (see Definition of terms) will also be shown. The denominator for the percentage is the total number of patients having data for the parameter per treatment and per analysis visit in the safety analysis set.

Laboratory toxicity grades will be presented as cross-tabulations (shift table) of the toxicity (NCI-CTCAE grades) at each post-baseline analysis visit and at the worst-case analysis visit versus the baseline toxicity. Numbers and cumulative numbers over decreasing toxicity grading of patients with treatment-emergent toxicities will also be shown. The denominator for the percentage is the total number of patients having data for the parameter per treatment and per analysis visit in the safety

SGS	Statistical Analysis Plan	
ARGX-113-1801	Final analysis	Final 1.0 of 28MAR2022

analysis set. Parameters having toxicity grades defined in both directions (hypo and hyper) will be shown by direction.

The tables will only show analysis visits as expected per SoA (including the followup phase).

All laboratory data will be listed, but only for patients with any post-baseline abnormality.

5.3 VITAL SIGNS

5.3.1 Available data

The following VS parameters are collected: systolic (SBP) and diastolic blood pressure (DBP) in supine position, pulse rate, body temperature and weight (weight will be measured at screening and at any IMP infusion visit).

5.3.2 Derivation rules

Abnormalities are defined in Table 11.

Table 11: Abnormalities for VS parameters

	Pulse rate (bpm)	SBP (mmHg)	DBP (mmHg)	Temperature (°C)
Low	<40	<90	<45	<35.8
Normal	40-100	90-150	45-90	35.8-37.5
High	>100	>150	>90	>37.5

Note: For the worst-case analysis visits, as defined in section 2.2.5, an additional category low + high is defined in case there are both low and high post-baseline values.

5.3.3 Presentation of results

VS parameters except weight will be summarized by means of descriptive statistics at each analysis visit. Actual values and changes from baseline will be shown in the same table.

Abnormalities will be presented as cross-tabulations of the abnormality at each postbaseline analysis visit versus the baseline abnormality and as cross-tabulations of the worst-case abnormality versus the baseline abnormality. Numbers of patients with treatment-emergent abnormalities will also be shown.

The tables will only show analysis visits as expected per SoA (including the followup phase).

All VS data will be listed, but only for patients with any post-baseline abnormality.

SGS	Statistical Analysis Plan	
ARGX-113-1801	Final analysis	Final 1.0 of 28MAR2022

5.4 ELECTROCARDIOGRAMS

5.4.1 Available data

The following ECG parameters will be collected: heart rate (HR), QRS interval, PR interval, QT interval, QTcF and QTcB.

5.4.2 Derivation rules

Abnormalities for HR, QRS and PR interval are defined in Table 12.

 Table 12: Abnormalities for ECG parameters

	HR (bpm)	PR (ms)	QRS (ms)
Low	<40	<120	-
Normal	40-100	120-220	0-120
High	>100	>220	>120

Note: For the worst-case analysis visit, as defined in section 2.2.5, an additional category low + high is defined in case there are both low and high post-baseline values.

For QTcF and QTcB interval (ms), the following categories are defined:

- Actual values:
 - $\circ \leq 450 \text{ (normal)}$
 - o]450; 480]
 - o]480; 500]
 - o >500
- Changes from baseline:
 - $\circ \leq 30 \text{ (normal)}$
 - o]30; 60]
 - o >60

Note: The worst-case, as defined in section 2.2.5, is the highest post-baseline value and associated change from baseline.

5.4.3 Presentation of results

Uncorrected QT interval and RR interval will only be listed.

Continuous ECG parameters will be summarized by means of descriptive statistics at each analysis visit. Actual values and changes from baseline will be shown in the same table.

Abnormalities of the actual values will be presented as cross-tabulations of the abnormality at each post-baseline analysis visit, and at the worst-case analysis visit versus the baseline abnormality. Numbers and cumulative numbers over decreasing abnormalities (QTcF and QTcB only) of patients with treatment-emergent abnormalities will also be shown. The denominator for the percentage is the total number of patients per treatment and per analysis visit in the safety analysis set.

SGS	Statistical Analysis Plan	
ARGX-113-1801	Final analysis	Final 1.0 of 28MAR2022

Abnormalities of the QTcF and QTcB changes from baseline will be presented as tabulations of the change from baseline abnormality at each post-baseline analysis visit and at the worst-case analysis visit. Cumulative numbers over decreasing change from baseline abnormalities of patients will also be shown. The denominator for the percentage is the total number of patients per treatment and per analysis visit in the safety analysis set.

The tables will only show analysis visits as expected per SoA (including the followup phase).

All ECG data will be listed, but only for patients with any post-baseline abnormality.

5.5 **PHYSICAL EXAMINATIONS**

